8.4.9. Other Safety Analysis

Not applicable.

8.7. Other Analysis

Not applicable.

9. SUMMARY OF INTERIM AND DMC ANALYSES

9.1. Interim Analysis

Throughout the enrollment period, a blinded interim look at the primary and secondary endpoint data may be conducted to evaluate the sample size assumptions. If such an interim assessment is scheduled, additional information will be provided in this section. Otherwise, no further details will be included.

11. LIST OF APPENDICES

APPENDIX A. SCHEDULE OF ASSESSMENTS

Sage Therapeutics, Inc. CONFIDENTIAL

Assessment	Screening						Treat	ment Pe	eriod						Follow	-up Period
Study Day	-28 to -1	1	3 (±1)	8 (±1)	15 (±1)	19 (±1)	29 (±1)	33 (±1)	43 (±1)	47 (±1)	57 (±3)	71 (±3)	80 (±3)	91 (+1) EOT	97 (±3)	104 (±3) EOS/ETV
Clinic Visit (CV)/Phone Call (PC)	CV	CV	PC	CV	CV	PC	CV	PC	CV	PC	CV	CV	PC	CV	CV	CV
Informed consent	x															
Inclusion/Exclusion	х	x														
Demographics	X															
Medical history	x	X														
Pregnancy test	X	X			x				x					X		X
	(serum; all women)	(unne; WOCBP only)			(urme; WOCBP only)	/		~	(urine; WOCBP only)					(urme; WOCBP only)		(urme; WOCBP only)
FSH (postmenopausal women only)	х															
Randomization ^a		x														
Drug screen	x	Х														
Complete physical examination, including neurological examination including MSE ^b	Х													х		Х
Body height	X															
Body weight	x	Х														X
Vital signs ^c	x	Х		Х	Х		х		Х		Х	х		Х	Х	X
12-Lead ECG ^d	x	X					x							Х		X
Chemistry/hematology/ coagulation/urinalysis ^e	Х	x		x	X		x		x		X	X		X		Х

Assessment	Screening						Trea	tment P	eriod						Follor	v-up Period
Study Day	-28 to -1	1	3 (±1)	8 (±1)	15 (±1)	19 (±1)	29 (±1)	33 (±1)	43 (±1)	47 (±1)	57 (±3)	71 (±3)	80 (±3)	91 (+1) EOT	97 (±3)	104 (±3) EOS/ETV
Participant training ¹	X	x														
Dispense IP		x			x		x		X		x	Х				
IP administration ^j				Adr	ninister	ed once	daily be	efore be	d on Da	y 1 thro	ugh Day	y 90				
AEs/SAEs, including COVID-19 assessments ^k									x							
Prior medication and history ¹	х															
Concomitant medication, diet, alcohol, and nicotine products									Х							
Abbreviations: AE = adver COVID-19 = coronavirus d treatment, termination visit; FSH = fol	se event; lisease 20 llicle stim	9; ulating	hormon	e ICF :	= inforr	ned cor	isent fo	rm: IP =	EC = invest	0G = ele	ectrocar al prodi	diogram ET = uct: MS	n EOS essenti E = me	= end c al trem ental sta	of study or; ET	; EOT = end / = early mination:
Essential Tremor Rating A: Note: The suggested order or assessments, and questionn	ssessment of assessm aires.	Scale; lents du	WOCBI tring cli	P = wor nic visit	nen of ts is vit	childbe al signs	aring po , TETR	otential. AS, EC	G, bloc	od samp	- are	sction fo	Dr	se even	ical lat	oratory
Note: If necessary, screenir therapy except propranolol ^a Randomization will occur ^b Complete physical examir clinically necessary (see Se ^c On Day 1, supine and stan	ng assessin during the on Day 1 nations an ction 12.1 ding bloo	ents m estreen after m 1 a com 1 a com	ay be sp ning Per ceting a prehens geted p ire and l	olit betw riod. Ill eligit ive neu hysical heart ra	een 2 v sility cr rologic and ner te will 1	visits in iteria. al exan urologic be colle	order t ination cal exar	o allow , includ minatior triplicar	enough ing MS is shoul te at lea	time fu Es, sho ld be pe ist 15 m	or wash ould be rrforme	out or d perform d at oth apart, m	lown-ti low at S loca at S er time neasure	itration Screenir s as ind ed after	and wang and wang and wang and the part the part	shout of pric EOT and as by AEs. ticipant has b
in the supine position for at Day 1.	t least 5 m	inutes a	ind then	repeate	od 1 mi	nute an	d 3 min	utes aft	er stand	ling. Re	spirato	ry rate a	und ten	nperatur	re are c	ollected once

^e Chemistry, hematology, coagulation, and urinalysis to be collected at all timepoints except Day 97. Note: Myoglobin (urinalysis) and serum creatine kinase (biochemistry) will be collected at Screening. In addition, myoglobin (urinalysis) and serum creatine kinase (biochemistry) may be collected at any ^d ECGs will be collected and read centrally. All ECGs must be performed after the participant has been in a supine position for at least 5 minutes.

additional timepoints at the discretion of the investigator (including Day 97). A serum sample for blood alcohol level will be collected at all timepoints includin Dav 97). HbA1c will be collected at Screening and EOS/ETV Visit only.

^g A videographer will record TETRAS administration at Screening.

^h Washout of prestudy ET drug(s) except propranolol after the ICF was signed (Protocol Section 9.2.2.1) must be completed prior to Screening TETRAS assessment.

receive 15 mg SAGE-324 from Day 1 to Day 14, then 30 mg from Day 15 to Day 28, then 45 mg from Day 29 to Day 42, and then 60 mg from Day 43 to ^j Will be administered once daily, to be taken before bed, with a snack if bedtime is not within 2 hours of the evening meal. The 60-mg dose group will Participants will be trained by study personnel on the use of software applications, IP diary, and devices necessary for the conduct of the study. Day 90.

¹Including all medications and supplements taken within the 30 days prior to signing the ICF through the first dose of IP, as well as a complete history of all ^k A phone call to follow up on any AE(s) will be conducted, if deemed appropriate by the investigator, to review the current status of the participant. treatments for ET since the year of diagnosis.

APPENDIX B. HANDLING OF MISSING DATES

Partial dates will adhere to the following conventions in order to classify TEAEs and to classify prior and concomitant medications.

In general, listings will present the actual partial or missing values rather than the imputed values that may be used in derivation.

Adverse Events

In the event of a missing/incomplete start or stop date associated with an adverse event, only the treatment-emergence will be imputed using the algorithm below. Dates will not be imputed.

In general, if the missing/incomplete start date is not clearly prior to initiation of treatment, then the AE will be considered a TEAE.

If the AE end date is prior to the initiation of treatment, the AE will not be considered a TEAE.

If the AE end date is on or after the initiation of treatment:

- If the AE start date is completely missing or if the year is missing, then the AE will be considered a TEAE
- For partial AE start dates:
 - Known year, unknown month and day (or known year and day, unknown month)
 - If the year is the same as or later than the year of the first dose, the AE will be considered a TEAE
 - Otherwise, the AE will not be considered a TEAE
 - Known year and month, unknown day
 - If the month and year are the same as or later than the month and year of the first dose, the AE will be considered a TEAE
 - Otherwise, the AE will not be considerd a TEAE

Prior and Concomitant Medications

No imputation process will be used to estimate missing data, except for the purposes of classifying medications as prior and/or concomitant. The following algorithms will be used for partially missing dates.

For start dates of medication uses:

• The day and month are missing: if the participant started receiving the study dosing in the reported year, the first dosing date will be used as the start date; otherwise '01 January' will be used as the start date.

- The day is missing: if the participant started receiving the study dosing in the reported month and year, the first dosing date will be used as the start date; otherwise, the first day of the reported month and year will be used as the start date.
- If the medication start date is completely missing, do not impute a date, but consider it as a concomitant medication, unless the medication end date is before the initiation of treatment, in which case the medication will be considered prior.

For stop dates of events or medication uses:

- The day and month are missing: if the study end date is in the reported year, the study end date will be used as the stop date; otherwise, '31 December' will be used as the stop date.
- The day is missing: if the study end date is in the reported month and year, the study end date will be used as the stop date; otherwise, the end of the reported month and year will be used as the stop date.
- If a medication has the stop date completely missing or missing the year, this medication will be considered as ongoing and concomitant. If a participant is missing a treatment start date, medication will not be classified as either prior or concomitant.

APPENDIX C. SAS CODE FOR ANALYSIS OF PRIMARY EFFICACY ENDPOINT

Example code for MMRM:

The ODS statement is used to create output datasets, particularly COVB, for subsequent MCP Mod analysis.

```
Proc mixed data=[input dataset name]
	method=reml covtest alpha=0.05;
Where CHG ne .;
Class SUBJID TRTP(ref='Placebo') AVISITN;
Model CHG = BASE TRTP AVISITN TRTP*AVISITN /
	htype=3
	ddfm=KENWARDROGER
	residual solution covb;
Repeated AVISITN / sub=SUBJID type=[desired covariance structure];
Lsmeans AVISITN * TRTP / cov pdiff cl alpha=0.05;
ODS output
	solutionf=[output dataset name]
	covb=[output dataset name];
Run;
```

Example code for imputation of monotone missing data:

```
Proc mi data = [input dataset name]
        out = monotone(rename=(_imputation_=impn))
        nimpute=20
        seed=XXXXXX
        min = . . 0 0 0 0 0 0 0 0
        max = . . 24 24 24 24 24 24 24 24
        round = . . 1 1 1 1 1 1 1 1;
    Var trtpn base
        avisitn8 avisitn15 avisitn29 avisitn43
        avisitn57 avisitn71 avisitn91 avisitn97;
    MCMC impute=monotone chain=multiple;
    EM maxiter=500 converge=0.00001;
    Run;
```

Example code for treatment-based imputation of non-monotone missing data:

Monotone regression(/details);
Run;

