8.3.1.1. Primary Efficacy Assessment

For the TETRAS Performance Subscale Item 4 (upper limb), three maneuvers/assessments will be completed for both arms, first for the right arm and then for the left, specifically Item 4a, limbs extended forward maneuver (postural tremor), Item 4b, wing-beating [elbows flexed] maneuver (postural tremor), and Item 4c finger-nose-finger maneuver (kinetic tremor). Each assessment is rated on a 0 to 4 scale of severity in 0.5-point increments, with higher scores indicating more severe tremor. The Performance Subscale Item 4 (upper limb) total score range for a given side (left or right) is 0 to 12, and for both sides combined is 0 to 24; if any component of a total score for a side or both sides is missing, the total score is not computed. Assessment of the TETRAS Performance Subscale Item 4 (upper limb) occurs at Screening and Days 1, 8, 15, 29, 43, 57, 71, 91/EOT, and 97.

The primary efficacy endpoint is the change from baseline in TETRAS Performance Subscale Item 4 (upper limb) total score at Day 91 in the monotherapy cohort for the Full Analysis Set.

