8.3.2. Visit Windows for Efficacy Analyses

The scheduled visits will not be windowed and will be used at nominal visit value for treatment and follow-up period visits (Day 1, Day 8, Day 15, Day 29, Day 43, Day 57, Day 71, Day 91, Day 97, Day 104). Unscheduled, end-of-treatment (EOT), and early termination visits (ETV) that happen on or before one day after the last dose will be mapped to a scheduled visit for analysis using the date of collection/assessment and Day 1, first dose date, as a basis to determine study day and then study day will be mapped to the intended visit according to the visit windows specified in the Table 2. Unscheduled, EOT, or ET visits that happen on or after 1 day after the last dose will be windowed using relative days since last dose date; the mapping will follow the visit window in Table 2. To accommodate as much data as possible into analysis, these windows have been widened relative to protocol-specified operational windows to have no gap between them; these windows are used for analysis purposes only.

Scheduled Visit	Study Day of Expected Visit	Study Day Window for Visit
Screening	Day -1	Days -28 to Day -1
Day 1 Predose	Day 1 Predose	Day 1 Predose
Day 8 (±1 day)	8	Day 1 Postdose to Day 11
Day 15 (±1 day)	15	Days 12 to 22
Day 29 (±1 day)	29	Days 23 to 36

Table 2:	Visit	Windows	for	Efficacy	Analy	vsis
				•		

Scheduled Visit	Study Day of Expected Visit	Study Day Window for Visit
Day 43 (±1 day)	43	Days 37 to 50
Day 57 (±3 days)	57	Days 51 to 64
Day 71 (±3 days)	71	Days 65 to 81
Day 91 (+1 day)	91	Days 82 to 96
Day 97/last dose +7 days (±3 days) 97/last dose+ 7 days		Days 97 to 100 (last dose+6 days, last dose + 10 days)
Day 104/last dose + 14 days $(\pm 3 \text{ days})(*)$	104/last dose + 14 days	≥ Day 101 (last dose + 11 days, last dose + 17 days)

Note: Parenthesized study days and study day windows are for unscheduled, EOT, and ET visits. For participants who have discontinued treatment prematurely with either unscheduled, EOT, or ET visits on or after 6 days of the last dose, those visits should be mapped to Day 97 or Day 104 using the parenthesized visit windows listed (ie, visit date – last dose date >1).

Note: (*) The scheduled visit of Day 104/last dose visit is for efficacy analysis excluding TETRAS.

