8.3.3.2. Sensitivity Analysis of Primary Endpoint

Sensitivity analysis of the primary endpoint will be performed to assess the robustness of the primary analysis results in the presence of missing data. For participants who terminate from treatment prior to the end of the analysis period due to adverse event, noncompliance with study procedures, death, physician decision, or use of a prohibited medication, missing measurements will be considered missing not at random (MNAR); for all other participants having missing measurements, missing values will be considered missing completely at random (MCAR).

For FAS monotherapy subjects having missing TETRAS Performance Subscale Item 4 (upper limb tremor) total score data at any visit, and, separately, for FAS subjects overall, all missing data (MCAR or MNAR) will be imputed via multiple imputation (50-100 iterations, depending on system run time) using treatment based regression methodology which includes baseline TETRAS Performance Subscale Item 4 (upper limb tremor) total score in the model, with minimum and maximum possible integer values of 0 to 24, respectively (example SAS code is found in Appendix C). The MMRM model, including the selected covariance structure, used for the main analysis of the primary efficacy endpoint will be repeated for each imputation, and the results combined and reported. The covariance matrices resulting from the MMRM run on each imputation will be combined into an overall covariance matrix will be passed to the MCP-Mod analysis to perform sensitivity analysis of the dose-response relationship. SAS code associated with this sensitivity analysis is noted in Appendix C.

If the sensitivity analysis yields a result/conclusion that is different from the result of the primary analysis, the nature of the discrepancy will be examined in order to clearly explain the discrepancy based on statistical principles, and the discrepancy will be discussed in the clinical study report.

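### The imputation code for the missing-data sensitivity analysis does not match the SAP's stated number of imputations, Item 4's half-point scale or the MMRM's treatment factor; the numerical effect is small

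*SAP*

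**What the plan says.** SAP 8.3.3.2 says that missing Item 4 totals will be "imputed via multiple imputation (50-100 iterations, depending on system run time) using treatment based regression methodology", with baseline in the model and imputed values limited to "minimum and maximum possible integer values of 0 to 24, respectively". It refers to Appendix C for example SAS code. The imputed data go through the MMRM, and the combined covariance matrix is passed to MCP-Mod. SAP 8.3.4 repeats the exercise for the secondary endpoint.

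In Appendix C the first PROC MI step is visible from start to end. It sets `nimpute=20`, uses the MCMC method with the option that fills only enough values to make the pattern monotone, opens its variable list with "Var trtpn base" followed by the eight post-baseline visits in order (Day 97 last), and rounds with "round = . . 1 1 1 1 1 1 1 1". It has no CLASS or BY statement. Of the second step, a monotone regression, only the closing lines appear in the text available.

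Two other sections matter. SAP 8.3.1.1 states of Item 4: "Each assessment is rated on a 0 to 4 scale of severity in 0.5-point increments". SAP 8.3.2 says of unscheduled, end-of-treatment and early-termination visits by premature discontinuers, six or more days after the last dose, that "those visits should be mapped to Day 97 or Day 104 using the parenthesized visit windows listed".

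**The concern.** This is the planned check of whether the primary result is robust to missing data, and it feeds MCP-Mod, whose subject is the shape of the dose-response. An imputation model with treatment as one numeric code can represent only a straight line across the codes. It is thus more restrictive than the MMRM it feeds, which takes treatment as a class factor. A check on shape should not lean toward one shape.

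The other two points concern traceability and scale. A programmer who follows the code does not deliver the number of imputations in the text. A programmer who follows either the code or 8.3.3.2 imputes on a coarser grid than the one on which the score is measured.

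**Working it through.** **1. Number of imputations.** Text: 50 to 100. Code: 20, which is 20/50 = 40% of the stated minimum. Relative efficiency is 1/(1 + FMI/m), where m is the number of imputations. The fraction of missing information (FMI) is not in the documents, so a range is assumed:

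| FMI | m = 20 | m = 50 | m = 100 |
|---|---|---|---|
| 0.15 | 0.993 | 0.997 | 0.999 |
| 0.30 | 0.985 | 0.994 | 0.997 |
| 0.40 | 0.980 | 0.992 | 0.996 |

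The standard error inflation at m = 20 is √(1 + FMI/20) − 1, or 0.4% to 1.0% for FMI 0.15 to 0.40.

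**2. Rounding.** Six ratings in 0.5-point steps give totals 0, 0.5, …, 24, which is 49 values, of which 24 are not whole numbers. The variable list and the rounding list each have 10 entries, so whole-point rounding applies to all eight post-baseline visits. Rounding to width w adds variance of about w²/12: 1/12 = 0.083 for whole points and 0.25/12 = 0.021 for half points. Against the planning variance 2.5² = 6.25 (SAP 5.2), these are 1.3% and 0.3%.

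**3. Treatment coding.**

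*Which values are affected.* Protocol 8.4.1 encourages participants who stop treatment to attend an end-of-treatment visit and a follow-up visit 7 days later. TETRAS is scheduled at Day 97, and 8.3.2 maps such late visits of discontinuers to Day 97 or Day 104. Because Day 97 is last in the variable list, a participant with a Day 97 score but no Day 91 score has a non-monotone pattern. The MCMC step then fills every earlier gap, including Day 91. The reach is therefore wider than stray missed visits.

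*How far a line can miss.* Take the Emax candidate under the SAP 8.3.3.1 guesstimates, with arm means −1.2, −2.7, −3.0 and −3.2, and assume codes 0, 1, 2, 3:

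- Slope = [(−1.5)(−1.2) + (−0.5)(−2.7) + (0.5)(−3.0) + (1.5)(−3.2)]/5 = −3.15/5 = −0.63. The mean is −2.525.
- Fitted values: −1.58, −2.21, −2.84, −3.47.
- Fitted minus true: −0.38, +0.49, +0.16, −0.27.

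Across the eight candidates the largest misfit is 0.51 points with codes 0 to 3, or 0.62 if the dose itself is the code. At the 15% non-evaluable rate in SAP 5.2, an arm mean moves by at most about 0.62 × 0.15 = 0.09. This rough ceiling ignores the observed visits, which also inform the imputation.

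*Allowing for the observed visits.* The multivariate normal was fitted by EM to large simulated samples (5,000 per arm, SD 2.5, within-participant correlation 0.7, half the effect left at Day 97, all discontinuers attending Day 97, codes 0 to 3). For an Emax-like shape with a 2-point maximum, the 15 mg difference from placebo shrank by about 0.06 points at 15% discontinuation and 0.15 at 35%. A separate run gave about 0.02 to 0.08 at 15% and up to about 0.17 at 35%. Abrupt plateau or umbrella shapes reached about 0.2 at 35%. With a flat truth the bias was within simulation noise.

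*Scale.* The pairwise standard error at 22 per arm is 2.5 × √(2/22) = 0.75. Biases of 0.08 and 0.17 are 0.08/0.75 = 0.11 and 0.17/0.75 = 0.23 of it.

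*Which repair.* With 26 per arm and 35% dropout, the root mean squared error against the full-data difference was 0.23 for the linear code, 0.25 for three arm indicators and 0.32 for MCMC run separately by arm. A by-arm run must estimate 9 means and 9 × 10/2 = 45 variances and covariances from about 26 people.

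**The case against.** The code is labelled as an example, has placeholders for dataset names and seed, and serves only a sensitivity analysis. The primary MMRM and MCP-Mod do not use it. That stands and limits the importance. It does not clear the code, because 8.3.3.2 refers to it for the method, 20 is not a placeholder, and the text does not say how treatment is coded.

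The 8.3.3.2 text speaks of iterations, which could be read as something other than imputations. However, it ties the number to run time, and no other visible setting lies between 50 and 100 (the EM limit is 500).

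Three stronger readings are tempting, and the documents do not support them.

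- *The code contradicts the SAP text throughout.* On rounding it follows 8.3.3.2, which itself asks for integers; the conflict is with the scale definition in 8.3.1.1. On treatment, the promise of treatment-based regression may describe the second step, whose procedure, class and variable lines are not visible, so that step cannot be judged.
- *The imputation manufactures a dose trend.* The model estimates a slope and does not impose one. If the true response is flat, the linear code is correctly specified and creates no trend. The possible effect is smoothing of a real, curved response.
- *MCMC should be run within each arm.* This removes the bias in large samples, but with 26 per arm it was less accurate than the linear code in every scenario simulated.

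**Conclusion.** Wrong as written, with a small numerical effect confined to the sensitivity analysis. The imputation count is a direct conflict between text and code. The rounding is a conflict within the SAP, with 8.3.3.2 and Appendix C on one side and 8.3.1.1 on the other. The numeric treatment code in the MCMC step is a mismatch with the MMRM that reaches Day 91 values of discontinuers with a Day 97 score.

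The count and rounding change precision by about 1% or little more. The treatment code biases differences from placebo by roughly 0.02 to 0.08 points at 15% dropout and up to about 0.17 at 35%, and by nothing when the response is flat or linear in the code. These figures rest on assumed codes 0 to 3 and on every discontinuer attending Day 97. The documents say only that attendance is encouraged, and the 35% rate is not theirs: they plan on 15% and name 20% as a trigger. The case for changing the code is that the changes are cheap and make a check on dose-response shape neutral about shape.

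**What to change.** - In SAP 8.3.3.2 and Appendix C, state one number of imputations in the planned range, for example 100, and call them imputations. Cost: run time.
- For Item 4, delete the word integer from 8.3.3.2 and set rounding to 0.5, or do not round. Do not carry 0.5 over to the ADL composite: after the rescaling in SAP 8.3.1.2 it is a sum of 11 + 2 = 13 whole-number scores with maximum 13 × 3 = 39, so its limits and rounding need their own line.
- In the MCMC step, replace `trtpn` by three arm indicators with placebo as reference. The variable list grows from 10 to 10 − 1 + 3 = 12, and the minimum, maximum and rounding lists must be extended to match. The price is slightly higher variance than the single code (0.25 against 0.23 in root mean squared error at 35% dropout). Do not run this step by arm.
- Confirm that Appendix C shows the second step in full with treatment as a class or indicator term, and apply the same correction there if it does not.

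In total this is a few lines of code and one sentence of text.
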